5.8. Statistical Analysis Plan

Raw data will be entered in SPSS version 20 software and analyzed using STATA version 13. Mothers with twins will be excluded from the analysis of birth outcomes. The sensitivity, specificity and predictive values will be calculated for microscopy and LAMP versus a gold standard of PCR. Statistical analysis of epidemiological variables and malaria positivity will be determined using univariate binomial regression. Variables found to be statistically significant with initial analysis will then characterized through multivariate analysis regression analysis. Risk ratios for primary outcome variables for intervention against standard of care arm will be calculated. Subgroup analysis will be done for potential confounders, and to compare positivity by LAMP and microscopy in the intervention arm.

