Primary objective:

The primary objective of this trial is to evaluate the effectiveness of LAMP-based enhanced malaria detection in improving pregnancy outcomes as measured by birth weight, neonatal anemia, maternal anemia, and stillbirth.

Secondary objective:

The secondary objectives are:

- a. To determine the proportion of asymptomatic MiP cases revealed by microscopy, RDT and LAMP
- b. To evaluate the impact of the intervention in terms of malaria-associated placental damage as evaluated by placenta weight and placental malaria.
- c. To evaluate the performances of IllucidX LAMP(ultrasensitive) compared to the approved method using the samples from the trial.
- d. To compare the diagnostic performance of microscopy, RDT and LAMP against qRT-PCR in MiP.
- e. To decipher parasitic genotypes that may impair diagnostic test performances and treatment efficacy using parasite whole-genome sequencing.

Section 3: Trial Methods

1. Trial design

The study is a prospective diagnostic study of malaria in pregnant women. The goal is to determine whether: (i) LAMP provides a clinically measurable benefit compared to current first-line diagnostic test of Giemsastained microscopy and whether (ii) enhanced case detection of asymptomatic mothers with LAMP has added value in terms of outcomes. We hypothesize that addition of LAMP to one arm will be of greater benefit than microscopy alone due to additional LAMP sensitivity. We further hypothesize that enhanced case detection by screening asymptomatic mothers at each antenatal visit will be of additional value in treating malaria. Both symptomatic and asymptomatic first and second trimester mothers will be included in the study and individually randomized to one of two arms: standard of care or enhanced cased detection arms using LAMP for malaria. Mothers will be enrolled during a twelve-months period from March 2021 to July 2022 then followed until 28 days after delivery

2. Randomization

Women will be screened for eligibility and randomized either in the Standard of Care (SOC, 1/3 of included women) arm or in the intervention arm (2/3 of included women).

Randomization will be implemented at each health center. Stratification per parity (primiparus, second pregnancy and \geq 3 pregnancy) will be implemented to avoid confounding factor of acquired immunity for MiP variants.

3. Sample size

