The sample size calculation for this study is based on detecting a difference in the proportion of deliveries with a low birth weight (LBW), which was felt to be the most clinically important outcome variable. The prevalence of deliveries with a LBW in Ethiopia was estimated to be 17.3%. An alpha of 0.05 was selected with an allocation ratio of 3:1 in favor of the enhanced case detection arm. The study will be powered to detect an absolute difference in the proportion of deliveries with a LBW of 5%, so a proportion in the enhanced case detection arm of 12.3% compared to 17.3% in the standard of care arm. Using a continuity correction and an attrition rate of 20%, a total sample size of 2583 is required to achieve 80% power.

4. Framework

The LAMPREG trial aims to show the superiority of the intervention arm.

5. Statistical Interim analyses and stopping guidance

a. Two formal interim analysis are planned

- One formal statistical interim analysis is planned when 25% of the total inclusion target number (n = 646) is reached. This interim analysis will focus on the inclusion baseline data and the follow-up data available to date.
- Another formal statistical interim analysis is planed when 25% of the inclusion target reached the end of the protocol (28 days post-natal delivery). This analysis will be partial since post hoc gold standard molecular testing will not be available yet.
 - b. Adjustments planned of the significance level due to interim analysis

The prevalence of malaria in the study sites is paramount for the study outcome. Interim analysis will tailor this factor and decision of site closure or site initiation may be taken.

c. Details of guidelines for stopping the trial early

The LAMPREG trial interim results will be presented to an advisory board. LAMPREG is not a new interventional drug trial, and therefore unlikely to be subject to study termination. The Ethiopian NRERC ethical board waived the need of independent data monitoring and safety committee for LAMPREG.

6. Timing of final analysis

The final analysis of clinical data in the SOC *vs.* LAMP arm will be performed after the last follow up is completed, in a time frame of 6 months (secund semester of 2022), given that data entry is performed according to the protocol.

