The laboratory testing post trial (gold standard testing, parasitic variant assessment) is scheduled for 2 years post sample collection, with analysis and publication of results within a 3-year frame (end of 2022- first semester of 2023).

7. Timing of outcome assessments

The scheduled of ANC visit is given in the study protocol (v1.5 – see table 5).

Section 4: Statistical Principles

1. Confidence intervals and p-values

All applicable statistical tests will be two-sided and will be performed using a 5% significance level.

All confidence intervals presented will be 95% and two-sided.

2. Adherence and Protocol Deviations

Protocol adherence is defined by the completion of all ANC visit as per study arm (included treatment course completion for women eligible) and the follow-up of the newborn for 28 days post-delivery.

Nonadherence is defined by the number of missed visits, the loss to follow-up or the absence of recorded birth weight.

Protocol deviation is defined as:

- Non-administration of malaria treatment for LAMP positive women in the intervention arm
- Incomplete treatment administration for any treated women
- Loss to follow up or partial course of ANC visit

3. Analysis population

The intention-to-treat population will include all randomized patients, according to the study arm they were randomized in.

Section 5: Trial population

1. Screening data

The following summaries will be presented for all screened patients: inclusion time frame, number of the screened expecting mothers, number of mothers recruited per month, the reason for non-recruitment. This summary will be presented overall and by study center.

2. Eligibility

Eligibility criteria are presented in the study protocol v1.5.

To summarize, all pregnant women >18 years old, with gestational age < 27 weeks and attending ANC care in any of the study centers is eligible to the study

3. Recruitment

The "CONSORT" diagram comprising the number of people screened, eligible, consented, randomized, receiving their allocated intervention (malaria diagnostic and treatment) and followed to delivery will be presented with the study results.

4. Withdrawal/Follow-up - level of withdrawal

The level of consent withdrawal will be tabulated (classified as "consent to continue follow-up, sample and data collection" "consent to continue follow up and data collection", "complete –no further follow-up or

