data collection", "lost to follow up". This will be presented in CONSORT diagram format rather than as a table, with numbers and reasons for withdrawal and/or exclusion from the analysis given at each stage. The numbers (with reasons) of losses to follow-up (dropouts and withdrawals) over the course of the trial will be summarized by treatment arm.

5. Population and subgroup to be analyzed

Intention-to-treat (ITT): All randomized study subjects. This will be the primary population for the analysis.

Per Protocol (PP): All randomized study subjects completing the whole study period (complete cases). For a specific analysis, study subjects with missing data on any of the variables in the model will be excluded from the analysis. Analyses of this population is seen as a sensitivity analysis to investigate whether conclusions are sensitive to assumptions regarding the pattern of missing data

We will analyze independently the following subgroups (Both ITT and PP populations):

- a. Primiparous mother
- b. **Asymptomatic malaria**: women who did not present symptom at any ANC visit but were detected positive for *Plasmodium* spp infection by any diagnostic method.
- c. **Sub microscopic malaria**: any women diagnosed positive for malaria by molecular method (LAMP or post hoc gold standard RT-qPCR)
- d. Malaria species identified: *P. falciparum*, *P. vivax* and mixed infections (3 subgroups)
- e. Women presenting positive malaria testing in placental blood at delivery
- f. Women from newborn with Low Birth Weight

6. Baseline patient characteristics

Expectant women will be described with respect to age, parity, gestity, gestational age, history of malaria, pregnancy complication, both overall and separately for the two randomized groups. These data will be summarized in a table.

Section 6: Analysis

1. Outcome definition

Primary study outcomes are related to newborn health: fetal anemia (hemoglobin <12.5 g/dL), mean birthweight, low birthweight (<2500 g), mean gestational age, preterm delivery (<37 weeks' gestation), mean birthweight for gestational age (Z scores), small for gestational age, fetal loss (spontaneous abortion at <28 weeks' gestation or stillbirth), and the composite outcomes of adverse livebirth (preterm, low

birthweight, or small for gestational age) and adverse pregnancy (adverse livebirth or fetal loss). Mortality outcomes included neonatal, perinatal, and mortality up to age 4 weeks.

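### SAP Section 5, item 5: first pregnancies are analysed alone, with no arm-by-parity interaction and without the other two randomised parity strata, so a chance difference in significance can be read as effect modification

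*SAP*

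**What the plan says.** SAP Section 5, item 5 (Population and subgroup to be analyzed) introduces its list with "We will analyze independently the following subgroups (Both ITT and PP populations". Item a is primiparous mothers. Items b to f are asymptomatic malaria, submicroscopic malaria, three species groups, women with a positive placental blood test, and women whose newborn had low birth weight (LBW).

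SAP Section 3, item 2 (Randomization) stratifies by first, second, and third or later pregnancy, and gives acquired immunity as the reason. The second and third strata are not in the subgroup list.

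No interaction or heterogeneity test appears in SAP Section 6, item 2 (Analysis methods), under Additional analyses (marked not applicable), or in Protocol 5.8. Protocol 5.8 adds only that "Subgroup analysis will be done for potential confounders", without naming them. SAP Section 4, item 1 sets the level: "All applicable statistical tests will be two-sided and will be performed using a 5% significance level". Section 6, item 2 promises a correction for multiple tests but gives neither its method nor its scope. Neither document gives a rule for interpreting subgroup results.

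**The concern.** A p-value within one subgroup tests whether there is an effect in that subgroup. It does not test whether the effect there differs from the effect elsewhere. The primiparous group is a minority of the sample, so it has much less power than the trial as a whole and will often miss significance when the effect is identical in all women.

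Parity matters in this trial. Protocol 5.3.1 says that in high-transmission settings harm from *P. falciparum* is greatest in first pregnancies, and the SAP stratifies on parity for a related reason. A non-significant primiparous result beside a significant overall result could be taken to mean that screening does not help first pregnancies, when the data show no such difference.

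**Working it through.** **Inputs**
- LBW rates: "so a proportion in the enhanced case detection arm of 12.3% compared to 17.3% in the standard of care arm" (SAP Section 3, item 3).
- Level: two-sided 5%, uncorrected, because the promised correction is unspecified.
- Allocation: the sample-size text says "An alpha of 0.05 was selected with an allocation ratio of 3:1 in favor of the enhanced case detection arm", but the randomisation text says "SOC, 1/3 of included women) arm or in the intervention arm (2/3 of included women". Both ratios were run.
- Primiparous share (assumption): neither document gives one for the trial. The pilots in Protocol section 3 had 22/87 = 25.3% and 13/34 = 38.2% first pregnancies.
- Effect (assumption): the same in every parity class.

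**Step 1. Reproduce the plan's own figure.** The plan states: "Using a continuity correction and an attrition rate of 20%, a total sample size of 2583 is required to achieve 80% power". With r = 3, d = 0.05 and pooled rate p = (0.173 + 3 × 0.123)/4 = 0.1355:
- n = [1.96·√((4/3)·p(1−p)) + 0.842·√(0.173·0.827 + 0.123·0.877/3)]² / 0.05² = 511.4 in standard of care.
- Continuity correction: (n/4)·[1 + √(1 + 2(r+1)/(n·r·d))]² = 537.7, so 538.
- Total 538 + 1614 = 2152, and 2152 × 1.2 = 2582.4, so 2583. This matches.

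Evaluable women are therefore 2152 as designed, or 2583 × 0.8 = 2066 if 20% of those enrolled are lost.

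**Step 2. Power in first pregnancies alone.** Take 2066 women, 3:1 and a 25.3% share, which gives 131 against 392 primiparous women.
- SE under no effect: √(0.1355·0.8645·(1/131 + 1/392)) = 0.0345.
- SE under the assumed effect: √(0.173·0.827/131 + 0.123·0.877/392) = 0.0370.
- Power = Φ((0.05 − 1.96 × 0.0345)/0.0370) = Φ(−0.48), about 32%, against about 80% overall.

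**Step 3. Simulate trials with one uniform effect.** 200,000 trials per row, 2066 women, two-proportion z-tests:

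| Ratio | Primiparous share | Overall p<0.05 | Primiparous p<0.05 | Overall significant, primiparous not | Exactly one of primiparous and the rest significant |
|---|---|---|---|---|---|
| 3:1 | 25.3% | 81% | 31% | 51% | 57% |
| 3:1 | 38.2% | 80% | 43% | 40% | 52% |
| 2:1 | 25.3% | 86% | 35% | 53% | 58% |
| 2:1 | 38.2% | 86% | 48% | 40% | 51% |

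With 2152 women, or a share of exactly 25%, the results hardly move. Over all cases the fifth column is about 40% to 54% and the last column 50% to 58%. The last column needs a test in the remaining women, which the plan does not list. The fifth column is the contrast the plan itself produces.

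**Step 4. The same data under an interaction test.** With one uniform effect, a heterogeneity test over two or three parity strata was significant in 5.0% to 5.3% of simulated trials.

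**Step 5. What that test can detect.** The SE of the difference in risk differences is √Σ(0.173·0.827/n_SOC + 0.123·0.877/n_LAMP), summed over primiparous and other women. With 2066 women, 3:1 and a 25.3% share it is 0.0428. Power for a 5-point difference is Φ(0.05/0.0428 − 1.96) = 21%. The difference detectable with 80% power is 2.80 × 0.0428 = 12.0 points. Over the four rows above, power is 21% to 30% and the detectable difference is 9.8 to 12.0 points.

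**The case against.** **The SAP does not say that differing p-values will be taken as effect modification.** This stands. It is silent on interpretation, so the documents support a risk of misreading and no more.

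**The 50% to 58% figure describes a comparison the plan does not make.** This also stands, which is why the main figure is 40% to 54%. A reader might infer that the likely error is a claim that screening works only in first pregnancies. The numbers do not support that: even if the remaining women were tested, primiparous women alone would be significant in only about 8% to 17% of trials. The reverse pattern is the common one.

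**A multiple-test correction is promised.** It is, and if applied it would reduce false positives, but it would not test heterogeneity. It could also widen the gap. Assume Bonferroni over the eight listed subgroups (level 0.00625, critical value 2.73) with the overall test left at 5%. Primiparous power in the Step 2 case falls to Φ((0.05 − 2.73 × 0.0345)/0.0370), about 12%. Overall significant with primiparous not then occurs in at least 80 − 12 = 68% of trials.

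**Site transmission.** A reader might infer that leaving it out is an error, because the SAP says "The prevalence of malaria in the study sites is paramount for the study outcome". That sentence is in the interim-analysis item and concerns closing or opening sites. The stated objectives concern overall impact. A transmission analysis is a reasonable addition, not a correction.

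**Protocol 5.8.** A reader might treat its reference to confounders as a second error. It is a matter of terminology, and it appears in protocol version 1.1, whereas the SAP is based on version 1.5, which is not among the documents.

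**An interaction test has little power here.** True. The gain is mainly a sound reporting rule.

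**Conclusion.** The concern holds for parity. The plan analyses one of three randomised parity strata by itself, has no test of whether the effect differs by parity, and gives no interpretation rule. If the effect is uniform, the overall result is significant and the primiparous result is not in about 40% to 54% of trials. An interaction test keeps the false-claim rate near 5%.

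These figures rest on the plan's own LBW rates, 2066 to 2152 evaluable women, an assumed primiparous share of 25% to 38%, and uncorrected 5% tests. The conflict between 3:1 and 2:1 needs reconciling but does not change the conclusion.

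A reader might infer that an interaction term would put the whole subgroup list right. It would not. Subgroups b to f are defined after randomisation: malaria detection depends on the testing done in each arm, placental infection can be affected by the intervention, and subgroup f is the primary outcome itself. Nor does the point reach the overall LBW comparison. It concerns secondary reporting and should be settled before arms are compared.

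**What to change.** 1. **State the by-arm LBW model in the SAP.** The risk ratios in SAP Section 6, item 2 are by malaria status. The risk ratio by randomised arm appears only in Protocol 5.8, so the SAP has no model to which an interaction can be added.
2. **Replace the separate analysis of subgroup a.** Add an arm by parity-stratum interaction over the three randomised strata. Report the risk ratio and 95% interval in every stratum with one interaction p-value, labelled exploratory.
3. **Add an interpretation rule.** No subgroup conclusion rests on a within-subgroup p-value.
4. **Label subgroups b to f descriptive.** They should not be used for treatment-effect claims.
5. **Optional.** Add a similar arm by site-transmission term, with levels fixed from the pre-trial health-ministry data mentioned in Protocol 5.1.

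The cost is SAP wording and one model term, with no new data. The drawback is low power: the usual result will be no evidence of a difference, and the report must not present that as evidence that the effect is the same in all strata.

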prospective fashion at three antenatal clinics. Our most complete data to date is from Jawi Health Centre in Amhara Region during the 2018 peak transmission season. In this study population, 28 of 34 pregnant women (mean age 24.2 years) who presented to the antenatal clinic were asymptomatic, 26 of 34 were in the first trimester, and 13 of 34 were primigravida. Malaria positivity amongst asymptomatic women was 3/34 (8.8%) by microscopy, 1/34 (2.9%) by RDT, 12/34 (35.3%) by commercial LAMP, and 12/34 (35.3%) by ELUCIDx, and 11/34 (32.3%) by qPCR. The sensitivity of microscopy in pregnant women in this study population was 25.0% (95% CI 5.49 - 57.19%), RDT 8.33% (0.21 - 38.48)), commercial LAMP 81.82% (48.22 - 97.72), ELUCIDx 100.00% (73.54 -100.00) and qPCR 91.67% (61.52 - 99.79) using a consensus gold standard. These data suggest that ultrasensitive diagnostics like LAMP are able to detect malaria far more frequently than traditional diagnostic methods when coupled to active case detection of symptomatic and asymptomatic pregnant women. The marked decrease in sensitivity for microscopy and RDT in phase 2 as compared to phase 1 is directly linked to the low level of infection found in asymptomatic pregnant women. We predict that greater detection of malaria in pregnancy with LAMP-based active case detection will lead to better critical outcomes such as LBW in pregnancy in the full-scale LAMPREG trial.

Table 3: Performance of LAMP compared to microscopy and rapid diagnostic tests (RDT) in asymptomatic and symptomatic pregnant women (N=34, Jawi, Amhara Region), phase 2 proof of concept prospective study with active case detection.

Method	Sensitivity % (95%CI)	Specificity % (95%CI)
Microscopy	25.00 (5.49 - 57.19)	100.00(84.56 - 100.00)
RDT	8.33 (0.21 - 38.48)	100.00(84.56 - 100.00)
Meridian LAMP (competitor)	81.82 (48.22 - 97.72)	86.96 (66.41 - 97.22)
ELUCIDx LAMP	100.00(73.54 -100.00)	100.00 (84.56 - 100.00)
qPCR	91.67 (61.52 - 99.79)	100.00 (84.56 - 100.00)

In additional preliminary data from Gojeb, Southwest Ethiopia, our study team has shown that treating pregnant women positive by LAMP has benefits in terms of fetal hemoglobin and birth weight, with the former reaching statistical significance (n=200, p<0.05). This is important data which requires confirmation in a full-scale trial across several epidemiological settings in Ethiopia.

Outcome			p Value
measure	LAMP Arm Mean (n=150)	SOC Arm Mean (n=50)	(t test)
Birth Weight (g)	3059	2965	0.1478

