symptomatic and asymptomatic first and second trimester mothers will be included in the study and individually randomized to one of two arms: standard of care or enhanced cased detection arms using LAMP for malaria. Mothers will be enrolled during a twelve-months period from October 2020 to October 2021 and then followed until 28 days after delivery. Given the rate of pregnant mothers at the locations, we anticipate that the required minimum of 2583 mothers will be enrolled in the study during the study period. In the first standard of care arm, venous blood sample will be collected from each study participant and the presence of *Plasmodium* infection will be diagnosed by microscopy in symptomatic patients. Pregnant women who test positive for malaria will be referred and treated for malaria with quinine or ACTs as per national guidelines. In the second (test) arm, mothers whether symptomatic or asymptomatic will be tested by a commercially available CE-approved LAMP malaria test (Meridien Biosciences, Illumigene Malaria M kit, Cincinatti, USA) and Human Diagnostics LoopAMP (Wiesbaden, Germany) at each clinic visit in addition to RDT/microscopy. The commercial LAMP tests can distinguish P. falciparum and P. vivax and treatment will be given according to national guidelines. The purpose of doing all tests in the intervention arm is to determine how many additional cases LAMP identified. The primary outcome is the proportion of deliveries with low birth weight, with secondary outcomes of: (i) absolute birth weight; (ii) maternal hemoglobin; (ii) neonatal hemoglobin at birth (Standard Hgb testing from peripheral blood or finger prick); (iv) neonatal mortality; (v) stillbirth; and (vi) prematurity in each of the two arms. Additionally, signs of current or past *Plasmodium* sequestration in the placenta will be evaluated.

[figure not shown]

Figure 1: Flowchart summarizing randomized trial

There will be a total of at least five antenatal visits (mandatory). Emergencies (medical consultation outside the planned visit) will be recorded for each included woman. Visit 1 and 2 may be combined for mothers who present in the second trimester. The following table summarizes the procedures to be conducted at each visit.

Visit #	Time frame	Aim	Action for the study
1	Visit at health care center	Inclusion	Enrolment and randomisation
2	26 weeks gestation	Follow up	Malaria testing as per inclusion arm (2mL venous blood on EDTA) +ANC regular care Maternal Hgb

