Regarding chloroquine, a cohort of 169 pregnant women treated by chloroquine in non-malaria endemic area did not show newborn abnormalities compared to placebo [34]. Recently, a study conducted in Malawi to evaluate the use of chloroquine for intermittent preventive treatment did not show any adverse effect in the 600 treated women compared to the standard of care IPT (sulfadoxine pyrimethamine) [35].

In regards of the recent literature and publications related to quinine, artemether lumefantrine and chloroquine during pregnancy, there is no major risk for treatment of women presenting asymptomatic *Plasmodium* spp infection. Importantly, *Plasmodium* spp infection, even asymptomatic and submicroscopic, has impact on birth outcomes.

Asymptomatic malaria is the presence of *Plasmodium* spp infection in peripheral blood in the absence of any symptom of the disease. During pregnancy, peripheral parasitemia are particularly low due to sequestration of infected erythrocytes in the placenta villosities [36,37]. The sequestration of the parasite in the placenta originates the negative birth outcomes associated with MiP : low birth weight, maternal anemia, abortion and stillbirth [38]. Estimation recall that 20% of stillbirth and 11% of all newborn death are direct consequences of MiP [39]. Both *P. falciparum* and *P. vivax* induce adverse pregnancy outcome. *P. falciparum* pathogenicity in MiP is well described [37,40] while the pathophysiology of *P. vivax* infection during pregnancy needs yet to be elucidated [41,42].

It is clearly demonstrated that pregnant women presenting asymptomatic or submicroscopic *Plasmodium* infection present more anemia than uninfected women [43]. A recent longitudinal study combining *Plasmodium* peripheral detection and placenta histology at delivery showed that

even women with only submicroscopic infection have an increased risk of placental malaria compared to women without any parasitemia [44].

[figure not shown]
For the above-mentioned reason, *Plasmodium* infection, even asymptomatic, present a risk for the mother health and fetal development.

Expectant mother safety is a priority during the LAMPREG trial. After *Plasmodium* spp infection diagnostic, final treatment choice will be at the discretion of the physician assessing the patient. Any pre-existing condition will be taken in consideration.

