6.0. WORK PLAN

7.0 English Version of Questionnaire Patient inclusion questionnaire

This questionnaire records both socio-demographic and clinical characteristics. For each question please give the answer carefully and clearly. The participant's name is not included in the questionnaire and their information will be kept completely anonymous and confidential. Their answers will be kept only by the study investigators and will not be distributed to anyone else.

Socio-demographic characteristics

- 1.1. ID no. of participant:
- 1.2. Age: _____ (Years)
- 1.3. Address:

1.4.	Are you currently pre	gnant?		A. Yes	B. No
1.5.	How many weeks pre	gnant are you	?		
1.6.	How many pregnanci	es have you ha	ad before this one?		
1.7.	Have you had any mi	scarriages or s	tillbirths before?	A. Yes	B. No
1.8.	If yes, how many?				
1.9.	Do you spend most ye	our time indoo	or or outdoor?		
A. Yes	s B. No				
1.10.	Has your house under	gone indoor r	esidual spraying in the last ?	3 months?	
A. Yes	s B. No				
1.11.	Do you sleep under in	secticide treat	ted nets?		
A. Ye	es B. No				
1.12.	Has anyone in your h	ousehold been	diagnosed with malaria in	the last montl	h?
A. Ye	es B. No				
1.13.	What is your level of	education?			
None	Primary	Secondary	Post-secondary		

Clinical characteristics

1. Does the participant have any of the following symptoms or signs?

Fever	A. Yes	B. No
Chills	A. Yes	B. No
Sweats	A. Yes	B. No
Headache	A. Yes	B. No
Muscle pains	A. Yes	B. No
Nausea	A. Yes	B. No
Vomiting	A. Yes	B. No
General malaise	A. Yes	B. No
Diarrhea	A. Yes	B. No

Does the participant have an axillary temperature greater than 37.5 degrees Celsius? 2. A. Yes B. No Does the participant have any signs of severe malaria?

3.

A. Yes B. No

4. Has the participant taken any anti-malarial medication in the last three weeks?

A. Yes B. No

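### The SAP defines the asymptomatic-malaria subgroup by symptoms over the whole pregnancy, not at the positive visit, so by-arm results in it are open to selection bias of uncertain direction

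*SAP*

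**What the plan says.** SAP Section 5, item 5 lists the subgroups to be analysed separately in both the ITT and PP populations. Subgroup b, asymptomatic malaria, consists of "women who did not present symptom at any ANC visit but were detected positive for" Plasmodium, whatever the test. The SAP does not say which symptoms count, or whether a symptom must coincide with the positive result.

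Protocol 5.12 uses the term differently: Plasmodium "infection in peripheral blood in the absence of any symptom of the disease". That describes an infection, not a whole pregnancy.

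SAP Section 2, item 2 relies on the term in secondary objective (a): "To determine the proportion of asymptomatic MiP cases revealed by microscopy, RDT and LAMP". No other part of the SAP defines asymptomatic infection by visit or by infection.

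The only symptom list is in the inclusion questionnaire (protocol 7.0), under the question "Does the participant have any of the following symptoms or signs". It covers fever, chills and sweats, but also headache, muscle pains, nausea, vomiting, general malaise and diarrhea.

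On follow-up, protocol 5.2 states: "There will be a total of at least five antenatal visits (mandatory". Table 5 counts delivery as visit 5, and visits 1 and 2 may be combined.

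**The concern.** Two things follow from judging symptoms over the whole pregnancy. First, a woman whose infection was silent when detected is removed by a symptom at any other visit, even one unrelated to malaria. Second, membership is settled after randomisation by events that the allocated arm can influence. In standard of care only symptomatic women are diagnosed in real time (protocol 5.2), so silent infections go untreated and some may become symptomatic. In the LAMP arm women are screened at each visit and treated if positive.

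At stake are the by-arm results in subgroup b and, if the same rule is used there, the count of asymptomatic cases for objective (a).

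**Working it through.** **Step 1: the definitions applied to the same women.** The examples use the visit weeks in Table 5. They assume that the questionnaire's list is what counts as a symptom. The last column is the SAP Section 6 definition of clinical malaria: fever, documented or reported, together with a positive RDT or microscopy.

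| Course | Protocol 5.12 | SAP subgroup b | Clinical malaria |
|---|---|---|---|
| Symptom-free and positive at 26 weeks, no symptom at other visits | asymptomatic | in | no |
| Same at 26 weeks; headache, negative test at 36 weeks | asymptomatic at 26 weeks | out | no |
| Control arm: same at 26 weeks (found later by qRT-PCR), untreated; fever and positive microscopy at 32 weeks | asymptomatic at 26 weeks | out | yes, at 32 weeks |
| LAMP arm: same at 26 weeks, treated; nausea recorded as a symptom at 32 weeks | asymptomatic at 26 weeks | out | no |

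Rows two and four fall between the SAP's own categories: neither asymptomatic nor clinical malaria. Rows three and four leave through routes that differ by arm.

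**Step 2: how many might be lost.** The documents give no figure for subgroup b, so there is nothing to reproduce. An illustration is possible.

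- Inputs: the Jawi pilot (protocol 3), where "28 of 34 pregnant women (mean age 24.2 years) who presented to the antenatal clinic were asymptomatic". This gives s = 28/34 = 0.8235 symptom-free at one visit.
- The woman was symptom-free at her positive visit by construction, so only the k other visits can remove her.
- Formula, with visits assumed independent: proportion dropped = 1 − s^k.
- Values of k: before delivery there are four visits, or three if visits 1 and 2 are combined, so k is 3 or 2. Counting delivery raises k to 4 or 3.

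Results:

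- k = 2: 1 − 0.8235² = 1 − 0.678 = 32%
- k = 3: 1 − 0.8235³ = 1 − 0.559 = 44%
- k = 4: 1 − 0.8235⁴ = 1 − 0.460 = 54%

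**Step 3: sensitivity to the symptom rate.** The pilot rate comes from 34 women at one site in peak season, and some of the six symptomatic women may have had malaria symptoms. Replacing 1 − s by an assumed rate q of 2% to 20% per visit for a symptom not due to malaria, 1 − (1 − q)^k gives:

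- k = 2: 4% to 36%
- k = 3: 6% to 49%
- k = 4: 8% to 59%

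Positive correlation of symptoms between visits lowers all these figures.

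**The case against.** Protocol 5.12 is background in an ethics section, not an analysis definition. The protocol at hand is v1.1, while the SAP was written against v1.5, which is not available here. The symptom list belongs to the inclusion questionnaire, and nothing says it is repeated at follow-up. The word symptom in subgroup b could mean symptoms of malaria only. Subgroup b is one of several secondary subgroups. Protocol objective 2, on screening asymptomatic mothers, is answered by the randomised comparison without it. Nothing states that its rule governs objective (a).

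Most of this stands as a limit on size and importance. It does not remove the problem. Even if only malaria symptoms count, the rule still looks across every visit, and a control-arm infection that turns symptomatic still moves the woman out.

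A reader might infer three stronger things that the documents do not support.

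- That the bias runs against the intervention, because the control arm keeps mainly infections that stayed silent. Protocol 5.12 lists nausea and vomiting among quinine's adverse effects. Both are on the symptom list, and women are encouraged to report side effects at the next ANC visit. That can remove treated LAMP-arm women too, so the net direction is unknown.
- That 44% to 54% are lost over three to four visits in total. That counts the positive visit again as one at which she could be removed; the correct range is 32% to 44%.
- That the trial's main result is affected. The primary population is all randomised women, and it does not use subgroup b.

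**Conclusion.** The concern holds as a defect in a secondary definition. As written, subgroup b excludes women who were symptom-free when positive, and selects on symptoms after randomisation that can differ by arm. By-arm results in it are therefore open to selection bias, with direction not established. Undercounting of asymptomatic cases for objective (a) is conditional on the same rule being used there. The primary comparison of low birth weight stands.

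The size cannot be computed from the documents. The illustrative loss of 32% to 44% (54% with four other visits) rests on the small pilot, on independence between visits, and on the questionnaire's list being applied at every visit. The change is worth making before analysis, but the trial's main conclusion does not depend on it.

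**What to change.** Reword subgroup b so that it classifies the infection: a positive sample with no listed malaria symptom recorded at that same visit. State in the SAP which symptoms count. Use this definition for objective (a), with infections as the unit.

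For any comparison by arm, define the subgroup identically in both arms by the post hoc qRT-PCR result and symptom status at the first study sample, before any result is acted on. Later symptoms and treatment then cannot move a woman in or out.

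This is mainly a wording change. Protocol 5.7.2 already collects dried blood spots from all individuals and plans qRT-PCR, and the current rule already needs symptoms by visit. Four costs or checks remain:

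- Table 5 lists no symptom recording by visit, so confirm that the data forms capture it.
- Table 5 shows only enrolment and randomisation at visit 1, with malaria testing from visit 2. The SAP must say which visit supplies the first sample.
- Infections first detected later fall outside the by-arm subgroup, although screening at each visit is the intervention. Report them descriptively.
- The by-arm subgroup result must wait for the post-trial laboratory testing.
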